4.3. Extent of Exposure

Extent of exposure to daratumumab will be summarized and presented based on the safety analysis set.

Duration of study treatment, defined as the number of days from the date of the first administration of study agents to the date of the last dose, will be summarized by descriptive statistics. The total dose administered for daratumumab (mg/kg) will be summarized by

treatment arm. In addition, the dose intensity of daratumumab (mg/kg/cycle) will be summarized for each treatment arm.

The number of subjects with dose delay including 1, 2 or >2 dose delays will be summarized by frequency. The reasons (AE or other) for dose delay will be reported.

Duration of follow-up calculated from the date of first dose of administration to the end of follow-up for each subject will be summarized for each treatment group and overall.

4.4. Protocol Deviations

Major protocol deviations will be summarized for the ITT population by the following types of deviations:

- Entered but did not satisfy inclusion/exclusion criteria
- Developed withdrawal criteria but not withdrawn
- Received wrong treatment or incorrect dose
- Received an excluded concomitant treatment
- Efficacy assessment deviation
- Other – protocol non-compliance

A list of subjects with major protocol deviations including subject ID, type of deviation, and protocol deviation coded term will be provided.

4.5. Prior and Concomitant Medications

The number and percentage of subjects who received prior systemic therapy will be summarized. Specifically, the summary will be presented by therapeutic class, pharmacologic class, and medication name.

Concomitant medication use will be summarized separately at baseline and during study treatment by therapeutic class, pharmacologic class, and medication name for each treatment group.

5. EFFICACY

5.1. Analysis Specifications

5.1.1. Level of Significance

For the co-primary endpoint of CR rate a 1-sided alpha of 0.05 will be used. For the co-primary endpoint of PD/death rate a 1-sided alpha of 0.1 will be used. No adjustments for multiplicity will be made.

5.1.2. Data Handling Rules

There is no imputation planned for missing efficacy endpoint values.

5.2. Primary Efficacy Endpoint(s)

5.2.1. Definition

There are two co-primary endpoints:

- Complete Response (CR) rate, defined as the proportion of subjects with a CR, as defined in Section 9.2.1.1 of the protocol
- PD/Death rate per patient-year, defined as number of events (PD or death)/total PFS for all subjects.

5.2.2. Analysis Methods

5.2.2.1. Complete Response

The number and percentage of subjects who achieve a complete response including 90% exact CI will be calculated for each treatment group based on response evaluable population. The exact p-value to test the hypothesis, H_0 : CR rate $\leq 15\%$ will also be calculated.

A similar analysis based on complete response based on investigator assessment will also be conducted.

5.2.2.2. PD/Death Rate

This will be considered as the second primary efficacy analysis and will occur one year after the last subject is randomized. The number of subjects with events (progression or death), total PFS and the PD/death rate per patient-year and the 80% confidence interval for the PD/death rate will be tabulated for each treatment arm. The p-value for testing the hypothesis, H_0 : PD/death rate ≥ 0.346 will also be calculated using a normal approximation.

5.3. Major Secondary Endpoints

The secondary endpoints include, minimal residual disease negative rate (not analyzed in this interim analysis), time to first treatment for active myeloma, overall response rate, progression-free survival, incidence of symptomatic MM with adverse prognostic features (not analyzed in this interim analysis), response to first active MM treatment and overall survival at 4 years.

5.3.1. Time to First Treatment for Active Myeloma

5.3.1.1. Definition

Time to first treatment for active myeloma is defined as the time from randomization to the start of subsequent antimyeloma treatment. Death due to PD without start of subsequent therapy will be considered as event. Subjects who withdrew consent to study or are lost to follow, or die due to causes other than disease progression will be censored at the date of death or the last date known to be alive.

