#### 9.2.2.2. Major Secondary Endpoints

- Minimal residual disease negative rate
- Time to next treatment defined as, the time from the date of randomization to the date of the first subsequent MM treatment
- Overall Response Rate defined as CR+PR rate
- PFS, defined as the time from the date of randomization to the date of initial documented PD according to the CRAB criteria, myeloma defining events, or date of death, whichever occurs first. For subjects who are progression-free and are alive at the time of data cutoff for an analysis, PFS will be censored at their last disease assessments on or before initiation of subsequent anti-MM therapy, lost to follow-up, or withdrawal of consent if any of them occurred, or last disease assessments if none of them occurred. PFS will be censored at the date of randomization if there is no postbaseline disease evaluation recorded.
- Incidence of symptomatic MM with adverse prognostic features, which include International Staging System (ISS) Stage III (based on  $\beta$ 2-microglobulin and albumin) and adverse cytogenetic characteristics
- Response to first subsequent MM treatment
- Overall survival rate

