### **11.3.2. Secondary Efficacy Endpoints**

The secondary efficacy endpoints are:

1. Minimal residual disease (MRD) rate: The number and proportion of subjects who have a negative MRD will be summarized for each treatment arm. An exact 90% confidence interval will also be calculated
2. Time to next treatment: The median TNT in each treatment arm will be estimated using the Kaplan-Meier method. A 90% confidence interval will also be calculated
3. Overall Response Rate defined as CR+PR rate: The number and proportion of subjects who achieve a CR or PR in each arm will be summarized. An exact 90% confidence interval will also be calculated.
4. PFS: The median PFS in each treatment arm will be estimated using the Kaplan-Meier method. A 90% confidence interval will also be calculated
5. Incidence of symptomatic MM with adverse prognostic features, which include International Staging System (ISS) Stage III (based on  $\beta$ 2-microglobulin and albumin) and adverse cytogenetic characteristics: The number and proportion of subjects with an incidence of symptomatic MM with adverse prognostic features will be summarized for each treatment arm. An exact 90% confidence interval will also be calculated
6. Response to first subsequent MM treatment will be summarized descriptively.
7. Overall survival rate

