### **16.2.3. Informed Consent**

Each subject (or a legally acceptable representative) must give written consent according to local requirements after the nature of the study has been fully explained. The ICF(s) must be signed before performance of any study-related activity. The ICF(s) that is/are used must be approved by both the sponsor and by the reviewing IEC/IRB and be in a language that the subject can read and understand. The informed consent should be in accordance with principles that originated in the Declaration of Helsinki, current ICH and GCP guidelines, applicable regulatory requirements, and sponsor policy.

Before enrollment in the study, the investigator or an authorized member of the study-site personnel must explain to potential subjects or their legally acceptable representatives the aims, methods, reasonably anticipated benefits, and potential hazards of the study, and any discomfort participation in the study may entail. Subjects will be informed that their participation is voluntary and that they may withdraw consent to participate at any time. They will be informed that choosing not to participate will not affect the care the subject will receive for the treatment of his or her

disease. Subjects will be told that alternative treatments are available if they refuse to take part and that such refusal will not prejudice future treatment. Finally, they will be told that the investigator will maintain a subject identification register for the purposes of long-term follow up if needed and that their records may be accessed by health authorities and authorized sponsor personnel without violating the confidentiality of the subject, to the extent permitted by the applicable law(s) or regulations. By signing the ICF the subject or legally acceptable representative is authorizing such access, including permission to obtain information about his or her survival status, and agrees to allow his or her study physician to recontact the subject for the purpose of obtaining consent for additional safety evaluations, if needed, and subsequent disease-related treatments, or to obtain information about his or her survival status.

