2.4.6. Partial First Anti-myeloma Therapy Start Date

The imputation rules for missing/partial start dates of subsequent therapies:

If year or month is missing or no components of the start date are present, no imputation will be performed.

If only the day-component is missing, the following steps apply:

- If the month and year of the start date are the same as the month and year of last dosing date, the day of last dosing date or the day-component of the stop date of subsequent anticancer therapy is imputed, whichever is earlier.
- If the start month and year are not the same as the month and year of last dosing date, the first day of the month is imputed.

If after the above imputation are applied, the imputed start date is after the non-imputed end date then re-adjust the start to be the same as the end date.

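### Time to next treatment has different events in protocol and SAP, and the SAP's last-known-alive censoring can credit treatment-free time nobody observed

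*SAP*

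**What the plan says.** **Protocol.** Section 9.2.2.2 (and the Synopsis) gives "Time to next treatment defined as, the time from the date of randomization to the date of the first subsequent MM treatment". Section 11.3.2 adds only the method: "The median TNT in each treatment arm will be estimated using the Kaplan-Meier method", with a 90% confidence interval. Death is not mentioned and no censoring rule is given.

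**SAP.** Section 5.3.1.1 changes the name and starts from the same event: "Time to first treatment for active myeloma is defined as the time from randomization to the start of subsequent antimyeloma treatment". It then adds "Death due to PD without start of subsequent therapy will be considered as event". The censoring rule covers "Subjects who withdrew consent to study or are lost to follow, or die due to causes other than disease progression", who "will be censored at the date of death or the last date known to be alive". Section 5.3.1.2 analyses the ITT set by Kaplan-Meier, with a median and 90% confidence interval per arm.

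**Partial dates.** SAP 2.4 lists the start of first antimyeloma therapy among the dates to be imputed, but SAP 2.4.6 says: "If year or month is missing or no components of the start date are present, no imputation will be performed".

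**Follow-up.** Under Protocol 9.1.4, subsequent therapy and survival status are collected together after progression, at least every 6 months. Protocol 16.2.3 describes the consent as "including permission to obtain information about his or her survival status". It mentions later disease treatments only in connection with recontacting the subject.

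**The concern.** Two things differ from what a reader of the protocol would expect.

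First, the event set. An added event type changes the endpoint, not merely its detail. Under the SAP an untreated death is an event or a censoring depending on its attributed cause, in an open-label study. The protocol has no such event.

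Second, the censoring date. A subject belongs in the risk set only while a start of therapy would be recorded if it happened. Being known alive does not ensure that. If survival is learned from a later source that is silent on treatment, the subject stays at risk during time in which no event could be seen, and the treatment-free curve is held up. The protocol applies the right principle to PFS, which is censored at the last disease assessment.

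At stake is a per-arm description of how long subjects remain off myeloma therapy. An arm with more withdrawals and longer gaps would look better than it should.

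**Working it through.** The documents give no power, event count or expected rate for this endpoint, so there is no plan figure to reproduce. The rates, withdrawal numbers, gaps and shares below are assumptions, except that 0.346 and 0.185 per patient-year are borrowed from the PD/death hypotheses (Protocol 2.2). Those match their stated medians: ln 2 / 2 years = 0.347 and ln 2 / 3.75 years = 0.185.

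**1. Event definition.** Let f be the share of SAP events that are progression deaths without therapy. Suppose the protocol definition censors them; the protocol does not say so. With constant hazards, the SAP median is ln 2 / rate and the protocol median is ln 2 / [rate × (1 − f)].

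| f | SAP median 24.0 months becomes | SAP median 45.0 months becomes |
|---|---|---|
| 2% | 24.5 | 45.9 |
| 5% | 25.3 | 47.3 |
| 10% | 26.7 | 50.0 |

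With f = 0 the definitions agree.

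**2. Censoring date.** Take 40 subjects, therapy start at λ = 0.30 per year, and k subjects whose therapy information stops at 0.5 year but who are censored g years later. True treatment-free probability at 2.4 years: exp(−0.30 × 2.4) = 0.487.

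During the gap the k subjects remain at risk but can have no recorded event. In expectation, with u = 0.5 + g (capped at 2.4), the estimate at 2.4 years is

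[(40 − k)·exp(−λu) + k·exp(−0.5λ)] / 40 × exp(−λ(2.4 − u)).

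- *No gap* (u = 0.5): the bracket reduces to 40·exp(−0.15), and the result is 0.487 for every k. Bias 0.
- *6-month gap* (u = 1.0), k = 6: (34 × 0.7408 + 6 × 0.8607) / 40 × 0.6570 = 0.499, or +1.2 points. For k = 2 and 4: 0.491 and 0.495, or +0.4 and +0.8.
- *24-month gap* (u capped at 2.4), k = 6: (34 × 0.4868 + 6 × 0.8607) / 40 = 0.543, or +5.6 points. For k = 2 and 4: 0.506 and 0.524, or +1.9 and +3.7.

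Simulated arms of 40 agree with these to within about 0.1 point. The sampling standard deviation of one arm's estimate is about 8 points.

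**3. The same effect on the median.** This used a large-sample simulation with 400,000 exponential times, withdrawal uniform over 0 to 4 years and cutoff at 5 to 7 years.

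| Withdrawn/lost | Gap | Median at 0.346/yr | Median at 0.185/yr |
|---|---|---|---|
| any | 0 | about 24 | about 45 |
| 10% | 12 months | 24.6 | 46.0 |
| 20% | 12 months | 25.2 | 47.3 |
| 20% | 24 months | 25.8 | 49.5 |

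With no gap the true median is recovered whatever the withdrawal share. Every gap moves it the same way, upward.

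**The case against.** The strongest case against the point is that the plan does not schedule any gap. After progression, therapy and survival status come from the same contact (Protocol 9.1.4). Before progression, subjects attend disease evaluations and no other SMM or MM treatment is allowed. The Follow-up Phase ends at withdrawal or loss (Protocol 3.1). Consent permits a survival look-up, but none is scheduled. Protocol 11 leaves specific details to the SAP, and the endpoint carries no test, alpha or planned between-arm comparison.

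Most of this stands, and it limits the size. It does not justify the rule: where the dates coincide, a correct rule gives the same answer; where they do not, the current one is wrong. Nor does leaving details to the SAP explain a new event type, which neither document reconciles.

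Four stronger readings are tempting but unsupported:

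- *The curve will be inflated by several points.* That needs something like a 24-month gap for every withdrawn subject. The documents do not say such gaps will occur.
- *The Phase 3 decision is affected.* Protocol 11.3 and 11.9 tie it to CR rate and PD/death rate.
- *Year-only therapy starts bias the curve upward.* SAP 2.4.6 leaves the date unimputed but does not say the subject is then censored as untreated. The handling is unstated, so the direction is unknown.
- *Death must be handled as a competing event.* This is a defensible preference, but both documents specify Kaplan-Meier medians, and the mismatch can be repaired within that method.

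**Conclusion.** The mismatch in events is certain from the text. Its effect depends on how many subjects die of progression untreated, which the documents do not give; it is nil if none do. The censoring rule is wrong in principle for this endpoint and can err in only one direction. Its size runs from nothing, when the last-alive and last-therapy-status dates coincide, to about 1 point at a gap equal to the 6-month contact interval, and up to about 5.6 points in an extreme 24-month case, all under the assumed rate and withdrawals at month 6. Except in the extreme case, this is small beside one arm's sampling error. It should be corrected, but it does not threaten the primary conclusions.

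A related omission: neither document says at what date a subject still in follow-up, alive and untreated at data cutoff, is censored.

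**What to change.** 1. Use one name and one event definition in Protocol 9.2.2.2, Protocol 11.3.2 and SAP 5.3.1.1. Report the other version as a sensitivity analysis. Keep the Kaplan-Meier method, and state how every untreated death is handled under each version.
2. Censor every untreated living subject, whether withdrawn, lost or still in follow-up at cutoff, at the last date known to be free of subsequent myeloma therapy.
3. Minor and unquantified: in SAP 2.4.6, state that a known start of therapy with only the year recorded counts as an event. Its imputed date should be no earlier than the last dose and no later than any known therapy end date, death or data cutoff.

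The cost is wording in two documents and some programming. No new data collection is needed, provided the date of each therapy-status contact is recorded.

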5.3.1.2. Analysis Methods

Analysis of time to first treatment for active myeloma will be based on the ITT analysis set. The Kaplan-Meier method will be used to estimate the distribution of time to first treatment for active myeloma for each treatment group. Median time to first treatment for active myeloma with 90%

CI will be provided. The Kaplan-Meier time to first treatment for active myeloma curve by treatment group will also be provided.

5.3.2. Overall Response Rate

5.3.2.1. Definition

ORR is defined as the proportion of subjects who achieve a partial response or better (i.e., PR, VGPR, CR or sCR) based on the computerized algorithm, according to IMWG response criteria, during or after the study treatment.

5.3.2.2. Analysis Methods

Analysis of ORR will be based on response-evaluable analysis set. The number and percentage of subjects in the following response categories will be presented by treatment group: stringent complete response (sCR), complete response (CR), sCR+CR, very good partial response (VGPR), partial response (PR), overall response (sCR+CR+VGPR+PR), stable disease (SD), progressive disease (PD), and not evaluable (NE). The corresponding 90% exact CI for each response category will also be provided.

A similar analysis based on complete response based on investigator assessment will also be conducted.

5.3.3. Progression-free Survival

5.3.3.1. Definition

Progression-free survival is defined as the time from the date of randomization to the date of initial documented PD according to the SLIM-CRAB criteria, or date of death, whichever occurs first.

5.3.3.2. Analysis Methods

Analysis of PFS will be based on the ITT analysis set. The Kaplan-Meier method will be used to estimate the distribution of PFS for each treatment group. Median PFS with 90% CI will be provided. In addition, the number and percentage of subjects who had a PFS event or were censored will be reported. The Kaplan-Meier PFS curve by treatment group will also be provided.

A similar analysis of PFS based on investigator assessment will also be conducted.

5.3.4. Response to First Active Multiple Myeloma Treatment

5.3.4.1. Definition

Response rate for first active multiple myeloma treatment is defined as the proportion of subjects who achieve a partial response or better (i.e., PR, VGPR, CR or sCR) as reported by the investigator, to their first active multiple myeloma treatment.

5.3.4.2. Analysis Methods

The number and percentage of subjects who achieve an overall response will be calculated for each treatment group based on population of subject who received active multiple myeloma treatment.

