**Table 1: Time and Events Schedule Overview**

As of Amendment 5, refer to [Attachment 4](#) for a description of dose administration and study procedures for subjects who continue in the Treatment Extension Phase or who have discontinued treatment but remain in Follow-up.

|   |  | Screening Phase                     | Treatment Phase (including treatment extension/re-initiation phase)                      | EOT                            | Follow-up |
|---|--|-------------------------------------|--|--------------------------------|-----------|
|   | Notes  | within 28 days before randomization | 8-week cycles  | at 28 ± 7 days after last dose |           |
| Study treatment should be initiated within 5 days after randomization. The start of each cycle may occur ±5 days of the scheduled day in order to accommodate the schedule of the site or subject. After EOT, subjects in all treatment arms prior to PD will continue to return for disease evaluations. After PD is documented, subjects will be followed for survival; subsequent anticancer therapy, and occurrence of other malignancy. Follow-up visits, unless otherwise specified, are at Week 5, Week 9, and then q8wks during the first year after subject's first dose, then q16wks until PD and q6mos after PD. |  |                                     |  |                                |           |
| Procedures   |  |                                     |  |                                |           |
| Informed consent  | ICF must be signed before any study-related procedures are performed.  | X                                   |  |                                |           |
| Eligibility criteria  |  | X                                   |  |                                |           |
| Demography/
Medical History  |  | X                                   |  |                                |           |
| Chest X-ray   | Acceptable for screening if performed as part of SOC within 42 days before randomization   | X                                   |  |                                |           |
| FEV1 test   | Subjects with COPD   | X                                   |  |                                |           |

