Even if a therapeutic approach is able to delay the progression to symptomatic MM, it will be important to establish whether the delayed symptomatic MM has a similar biology, responsiveness to standard therapy approaches, and outcomes as compared with watchful waiting. Within the constraints of a randomized Phase 2 design, data (including cytogenetics) will be collected on the biologic characteristics of the myeloma, the response to frontline therapy, and overall survival (OS).

[figure not shown]

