#### 9.1.4. Follow-up Phase

The Follow-up Phase will begin once subjects complete the planned number of cycles, and no treatment extension will be given as per investigator's discretion. In case of treatment extension or treatment re-initiation, the same procedures are to be followed as outlined in Section 9.1.3 and Table 1 (as of Amendment 5, refer to Attachment 4). If included in the treatment extension, it is possible that subjects will have 2 Follow-up Phase portions of the study (1 after the planned 20 cycles, and 1 after the last dose in the treatment extension). As of Amendment 5, these additional protocol-specified Follow-up assessments should be conducted as specified in Attachment 4.

Reasons for premature discontinuation of study treatment are listed in Section 10.3. Subjects who discontinue before disease progression must continue to have disease evaluations at Week 5, Week 9, and then every 8 weeks for the first year, thereafter every 16 weeks according to the Table 1 (as of Amendment 5, refer to Attachment 4) until confirmed PD, death, the start of a new anticancer therapy, withdrawal of consent, lost to follow-up, or the end of the study. If subjects have not progressed to symptomatic MM, no other treatment for SMM or MM is allowed during the study. After progressive disease, follow-up for subsequent multiple myeloma therapy (including the response to the first subsequent multiple myeloma therapy), second primary malignancies, and survival status will be obtained at least every 6 months.

If the information is obtained via telephone contact, written documentation of the communication must be available for review in the source documents. If the subject has died, the date and cause of death will be collected and documented in the eCRF.

The end of the study will occur up to approximately 7 years after the last subject's first dose, following a decision by the sponsor to end the study based on data from the smoldering multiple myeloma Phase 3 study (SMM3001), or for reasons outlined in Section 17.9.2, whichever occurs first.

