### **9.2.1.9. Best Response to First Subsequent Anti-myeloma Therapy**

Best response to first subsequent anti-myeloma therapy will be assessed by physician report at 6-month intervals. IMWG response criteria for MM will be used for these assessments.

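### Response to first myeloma treatment is divided by everyone treated by the cutoff, including subjects too recently started to have a response report due, so the rate is biased downward at the interim and 12-month analyses

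*SAP*

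**What the plan says.** SAP 5.3.4.1 defines the endpoint as the proportion with partial response or better "as reported by the investigator, to their first active multiple myeloma treatment". SAP 5.3.4.2 sets the denominator: the calculation is "based on population of subject who received active multiple myeloma treatment". Neither section requires a minimum time on therapy or a response report, and neither provides a not-evaluable category. SAP 5.1.2 adds only that "There is no imputation planned for missing efficacy endpoint values".

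The data come from follow-up contacts. Protocol 9.2.1.9 states: "Best response to first subsequent anti-myeloma therapy will be assessed by physician report at 6-month intervals". Protocol 9.1.4 is looser: after progression, subsequent therapy and the response to it, "second primary malignancies, and survival status will be obtained at least every 6 months". Protocol Table 1 starts that clock at progression, with visits "then q16wks until PD and q6mos after PD".

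SAP 5.3 lists the secondary endpoints and marks two of them, MRD negativity and adverse-feature myeloma, as left out of the interim. The next item carries no such mark: "incidence of symptomatic MM with adverse prognostic features (not analyzed in this interim analysis), response to first active MM treatment".

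**The concern.** Subjects reach this endpoint's starting point late and at scattered times, since each must first progress and then begin therapy. At a cutoff 6 or 12 months after the last randomization, many of those treated will have started only recently. Read literally, SAP 5.3.4.2 puts them in the denominator, and they cannot enter the numerator until a response is reported.

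Other SAP analyses are protected against this. The response-evaluable set (SAP 2.5.1) requires a post-baseline disease assessment, ORR (SAP 5.3.2.2) has a not-evaluable row, and the time-to-event endpoints use Kaplan-Meier estimation. This response rate has no equivalent.

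What is at stake is interpretation. Protocol 3.2 gives the purpose: "it will be important to establish whether the delayed symptomatic MM has a similar biology, responsiveness to standard therapy approaches". A reporting delay that makes emerging myeloma look less responsive pushes the answer in the unfavourable direction. The 12-month data go into the Clinical Study Report.

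**Working it through.** **Inputs from the documents.** 40 subjects per arm; PD/death rate 0.185 (alternative) or 0.346 (null) per patient-year; cutoffs 6 and 12 months after the last randomization; contacts at least every 6 months after progression.

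**Assumed, because not stated.** Uniform accrual over A = 6 to 24 months; exponential event times; every PD/death event leads to therapy; therapy starts 0 to 3 months after progression.

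**Check on the model.** The plan gives no figure for this endpoint. The nearest is the 80% power for the PD/death rate (SAP 1.4). With A = 9 months and rate 0.185, expected follow-up to the 12-month cutoff is 48.4 patient-years per arm. Using the null variance, the one-sided 0.1 critical value is 0.346 − 1.2816 × √(0.346/48.4) = 0.2377. Power is Φ[(0.2377 − 0.185)/√(0.185/48.4)] = Φ(0.85) = 80%. Accrual of 6 and 12 months gives 77% and 83%. The model is consistent with the plan.

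**Formula.** Let F(t) = 1 − exp(−λt), with F = 0 for t < 0. Let t be a subject's follow-up, uniform from f to f + A, where f = 1 year or 0.5 year. With therapy starting L after progression and a wait w from therapy start to the first due report, the share of starters without a due report is

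[mean F(t − L) − mean F(t − L − w)] / mean F(t − L).

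**Worked cases, A = 12 months, λ = 0.185.**

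- 12-month cutoff, L = 0, w = 6 months: mean F(t) = 0.2412 and mean F(t − 0.5) = 0.1677. Share = 0.0735/0.2412 = 30%. Expected starters: 40 × 0.2412 = 9.6 per arm.
- Interim, L = 0, w = 6 months: 0.1677 and 0.0871. Share = 0.0806/0.1677 = 48%.
- 12-month cutoff, contact 6 months after progression, L = 2 months, so w = 4 months: 0.2175 and 0.1677. Share = 0.0498/0.2175 = 23%.

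**Ranges over A = 6 to 24 months and both rates.**

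| Reporting assumption | 12-month analysis | Interim |
|---|---|---|
| Full 6-month wait, therapy starts at progression | 20-37% | 29-65% |
| Contacts from progression, therapy 1 month later | 17-33% | 26-61% |
| Same, 2 months later | 14-29% | 22-56% |
| Same, 3 months later | 11-23% | 18-49% |

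At study end under the first row's assumptions, the share is about 1-3% at the protocol's 7 years. At the 4 years still written in SAP 1.2 it is about 5-8% (accrual 6-18 months).

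Expected starters are at most about 8-20 per arm at 12 months and 5-16 at the interim. Deaths do not start therapy, and subjects progressing on free light chain criteria alone may stay on study drug (Protocol 9.2.1.3), so actual numbers would be lower.

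**From share to bias.** If a share s has no report and the true response probability is p, the displayed rate is p(1 − s) and the shortfall is p × s. With p = 80% assumed and s = 11-33%, the display would be 71% down to 54%. This too is a ceiling: it assumes that none of those subjects has an early report and that all are already in the denominator.

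**The case against.** The strongest objection is about how the data arrive. Protocol 9.1.4 collects subsequent therapy and its response at the same follow-up, and the Table 1 row for subsequent therapy asks for both together. If no contact has taken place since therapy began, the therapy itself may be unrecorded, and the subject is then in neither numerator nor denominator. The calculation above counts every starter at once. This stands: it lowers the shares by an amount the documents do not allow one to calculate. It does not remove the problem, because therapy may become known by another route, or a first contact may come too early for a response to have developed.

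A reader might infer that 20-37% of treated subjects at 12 months and 29-65% at the interim will be counted as non-responders. The documents do not support that, for three reasons. Reports are due at least every 6 months, so 6 months is the longest gap. The clock runs from progression, so the wait after therapy start can be shorter. And some subjects without a report will be true non-responders.

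A reader might also infer that the SAP instructs that a missing response be scored as failure. It does not. It is silent; the effect follows from dividing by all treated subjects.

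Finally, the consequence is limited. Protocol 11.3.2 makes the endpoint descriptive, SAP 5.3.4.2 specifies no test or interval, and the Phase 3 decision rests on CR and PD/death rate. That also stands.

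**Conclusion.** The point holds as a gap in the SAP with a known direction and an uncertain size. The stated denominator biases the rate downward at the interim and 12-month analyses, and the interim is not exempted. The upper limits, 20-37% and 29-65% without a due report, require therapy at progression, immediate knowledge of every start and a full 6-month wait for each subject. With contacts counted from progression and therapy 1-3 months later, the shares are about 11-33% and 18-61%. They are lower still where therapy start and response are learned at the same contact. All of these rest on assumed accrual of 6-24 months.

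The effect nearly disappears by a 7-year study end, and no error rate is affected. Nor is there support for reading it as a meaningful distortion between arms: at the same accrual length, the two event rates give shares only about 1-2 points apart. The matter is modest, but with so few treated subjects per arm, two or three without a due report would visibly move the 12-month percentage.

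**What to change.** - In SAP 5.3.4.2, calculate the rate among subjects who started first active myeloma treatment at least 6 months before the data cutoff, whether or not an assessment or death has been recorded. By then at least one contact is due. Subjects with no report stay in this denominator as NE.
- Show the all-treated rate alongside, with a separate count of subjects who started less than 6 months before the cutoff or are not yet assessed.
- In SAP 5.3, give this endpoint the interim exclusion that two others already carry, or present it at the interim as a listing only.

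Admitting recent starters only when they already have an assessment or have died should be avoided, because inclusion would then depend on outcome and on reporting.

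The cost is SAP wording, an extra table row or two, and precision at 12 months. In the worked case the expected denominator falls from 9.6 to 40 × 0.1677 = 6.7 per arm. Across the scenarios with therapy at progression the loss is 20-37%, and somewhat more if therapy starts later. At study end almost nothing is lost.
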